6.11.6 Supplementary Analyses

Analysis of Section 6.11.2 will be repeated for the Per Protocol population.

Additional analysis will investigate the treatment effect on PRO TSS change from baseline in the subgroups defined in Section 5.9. This analysis will use ANCOVA similarly to the primary analysis (Section 6.11.2).

Empirical cumulative distribution function (eCDF) of the change from baseline in TSS will be plotted by treatment group to demonstrate consistency of the treatment effect.

6.12 Analysis of Secondary Efficacy Endpoints

6.12.1 Change in Tissue Eosinophil Count

For subjects who provide gastric or duodenal only biopsy, the calculation will be based on the average count of the highest readings from the respective mucosa at baseline and Day 169 (Week 24). For subjects who provide both gastric and duodenal biopsies, the calculation will be based on the average count of the highest readings from the Day 169 biopsy that corresponds in location (gastric or duodenal) to the location with the highest average count at baseline. The change in tissue eosinophil count from baseline to Day 169 will be analyzed using ANCOVA with treatment as factor, baseline eosinophil counts, baseline PRO TSS, and disease status as covariates. The LSM, SE, and 95% CI for individual treatment groups, and LSM, SE, 95% CI, and p-value for the between treatment difference will be presented.

6.12.2 Proportion of Subjects Achieving Peak Gastric and/or Duodenal Intraepithelial Eosinophil Count of ≤ 1 Cell/hpf

This endpoint will be analyzed using the Fisher's exact test similar to the analysis for the first co-primary endpoint (Section 6.11.1).

6.12.3 Proportion of Treatment Responders

Treatment responder is defined as $>30\%$ improvement in TSS and mean eosinophil count ≤ 4 cells/hpf in 5 highest gastric hpf and/or mean eosinophil count ≤ 15 cells/hpf in 3 highest duodenal hpf. This endpoint will be analyzed using Fisher's exact test similar to Section 6.11.1.

6.12.4 Proportion of Subjects with $\geq 50\%$ Reduction and $\geq 70\%$ Reduction in TSS from Baseline to Weeks 23–24

These 2 endpoints will be analyzed using the CMH test stratified by the randomization stratification factors.

6.12.5 Change in Weekly TSS Over Time

Prior to the analysis, the missing weekly TSS scores will be imputed similarly to the imputation for the missing biweekly PRO TSS scores (Section 5.4.2). The imputed data sets will be analyzed using the mixed model for repeat measures (CCI [REDACTED]) with treatment, week, and treatment-by-week interaction as fixed factors, baseline PRO TSS (continuous), and EoD without EG (Y/N) as covariates, and subject as repeated measure unit over time. The model will use change from baseline in the weekly TSS from Weeks 1 through Week 24.

The model variance-covariance matrix will be unstructured. If the computation does not converge, the covariance matrix will take the form of Toeplitz, AR(1), and compound symmetry, whichever converges first. The improved Kenward-Rodger's method (SAS KR2 option) will be used to derive the denominator degrees-of-freedom. The LSM and 95% CI for the between group difference will be estimated using the simple contrast at each week.

A sample SAS code is provided as follows.

```
proc mixed data=ADEF method=REML ;
  class TRTPN USUBJID WEEK ;
  model CHG = B_TSS DISEASE_STRAT TRTPN WEEK TRTPN*WEEK / ddfm=KR2 ;
  repeated WEEK / subject=USUBJID(TRTPN) type=UN ;
  lsmeans TRTPN*WEEK / pdiff cl ;
run ;
```

The rationale for using the CCI [REDACTED] model is that this analysis is appropriate assuming subjects with missing data behave similarly to other subjects in the same treatment group. Having included in the model baseline symptom score (TSS), disease status (EG \pm EoD vs. EoD), and response trajectory prior to missing, it is reasonable to believe that the missing data are either completely at random (MCAR) or at random (MAR) in this setting. In another words, if missing mechanism is not MCAR, it is likely explainable by the above model covariates and response trajectory. A sample SAS code is included in [Appendix 4](#).

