3.2.3 Methods of Assigning Subjects to Treatment Group

Approximately 160 subjects with symptomatic EG and/or EoD will be stratified by baseline TSS and disease status (EG \pm EoD, EoD). Subject will be randomized 1:1 to receive 1 of 2 dose regimens using stratified randomized blocks in a double-blind manner.

- AK002 at 1 mg/kg for the first dose followed by 3 mg/kg administered every 4 weeks for 5 subsequent doses.
- 6 doses of placebo

It is anticipated that at least 90 subjects with EG \pm EoD will be enrolled, and up to 70 subjects with EoD without EG will be enrolled.

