3.5 Determination of Sample Size

A total of approximately 160 subjects will be enrolled.

First Co-Primary Endpoint: A sample size of 80 subjects per treatment group will have >99% power to demonstrate a greater proportion of tissue responders at Week 24 in AK002 subjects when compared to placebo subjects, assuming the proportions of responders are 0.6 and 0.1 in AK002 and placebo groups, respectively.

Second Co-Primary Endpoint: A sample size of 80 subjects per group will provide 96% power to detect a statistically significant difference of 7.4 points between AK002 and placebo in the mean reduction from baseline in TSS at Weeks 23–24, assuming a common standard deviation of 12.5 points and a population mean baseline TSS of 30 points.

4. Definitions

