5.8 Multiple Comparisons/Multiplicity Adjustment

To control for the family-wise type-I error rate, the following testing procedures will be implemented:

Test each co-primary efficacy endpoint at 2-sided $\alpha=0.05$ level.

- If $p\leq 0.05$ for both co-primary endpoints, then reject the null hypothesis that AK002 is no different from placebo and accept the alternative hypothesis that AK002 is superior to placebo in reducing tissue eosinophil count and TSS score.
- If $p\leq 0.05$ for both co-primary endpoints, the hypothesis tests for the secondary endpoints will proceed in the prespecified order.
- If $p>0.05$ for either co-primary endpoint, the null hypothesis is accepted. No hypothesis test will be performed for the secondary endpoints.
- The issue of multiplicity of secondary endpoints will be handled by statistical testing of these outcomes in a hierarchical fashion. The order of secondary endpoints is described in Section 2.2. If at any point during the analysis of the secondary endpoints, the statistical test is not significant at 2-sided $\alpha=0.05$ level, the hypothesis testing procedure will stop. AK002 will be deemed superior to placebo for all endpoints prior to the stop.

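### If the 24-week unstructured model fails to converge, every fallback in SAP 6.12.5 imposes one variance on all weeks, so the weekly intervals are miscalibrated if the variance of change differs by week

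*SAP*

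**What the plan says.** SAP 6.12.5 analyses weekly TSS with a repeated-measures mixed model after missing weekly scores have been imputed. On the outcome it says: "The model will use change from baseline in the weekly TSS from Weeks 1 through Week 24". On the covariance: "The model variance-covariance matrix will be unstructured". The contingency is: "If the computation does not converge, the covariance matrix will take the form of Toeplitz, AR(1), and compound symmetry, whichever converges first".

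The sample code has the model line "model CHG = B_TSS DISEASE_STRAT TRTPN WEEK TRTPN*WEEK / ddfm=KR2" with an unstructured repeated statement. It has no option that would let the variance differ by week under another structure, and no robust variance. A treatment contrast with a 95% CI is reported at each week.

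Protocol 15.6.2 names only the unstructured form, so the fallback list is the SAP's own. Weekly TSS comes last among the secondary endpoints in SAP 2.2, which SAP 5.8 makes the testing order.

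**The concern.** Toeplitz, AR(1) and compound symmetry, as named, differ in how they model correlation between weeks, but each has a single variance for all weeks. The standard error of the Week 1 contrast and of the Week 24 contrast then rest on the same pooled variance. KR2 adjusts for estimating the covariance parameters. It does not repair a structure that is wrong.

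The outcome is change from a baseline taken over the last two weeks before dosing (SAP 4.1). Week 1 lies next to that baseline and Week 24 about six months from it, so unequal variances are plausible. If they occur, the reported weekly intervals do not have their stated coverage. The SAP also does not say whether one structure must be used for every imputed data set. If some fits converge and others do not, results from different structures could be pooled.

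**Working it through.** **Inputs from the plan.** Two-sided 0.05 (SAP 5.8: "Test each co-primary efficacy endpoint at 2-sided $\alpha=0.05$ level"); 80 per arm, 1:1 allocation (SAP 3.5 and 3.2.3); SD of change "assuming a common standard deviation of 12.5 points", given for Weeks 23–24 only; 24 weekly time points.

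**The plan's own figure.** SAP 3.5 states: "A sample size of 80 subjects per group will provide 96% power to detect a statistically significant difference of 7.4 points". The standard error of the difference is 12.5 × √(2/80) = 1.976, and 7.4/1.976 = 3.744. Power is about Φ(3.744 − 1.960) = Φ(1.784) = 0.963, or 0.961 with the noncentral t on 158 degrees of freedom. The stated 96% is reproduced.

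**Covariance parameters.** Unstructured: 24 × 25/2 = 300. Toeplitz 24, AR(1) 2, compound symmetry 2. With week-specific variances: TOEPH 47, ARH(1) 25, CSH 25. That is 23 more in each case.

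**Effect of a common variance.** With complete (imputed), balanced data and a mean for every treatment-by-week cell, the Week t contrast is close to a difference in means. Its correct standard error is SD_t × √(2/80). Under a common variance it is about s × √(2/80). The ratio is therefore s/SD_t. For compound symmetry, s is the root mean square of the 24 weekly SDs. The error rate of one Week 24 contrast is 2 × [1 − Φ(1.96 × ratio)].

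The documents give no SD of change by week. The paths below are assumptions that all end at 12.5. That figure stands in for the single-week residual SD at Week 24, and only the relative size across weeks matters. For 24 equally spaced SDs, the mean square is (midpoint)² + (range²/12) × 25/23.

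- Linear 6 to 12.5: 9.25² + (6.5²/12)(25/23) = 85.56 + 3.83 = 89.39; s = 9.45; ratio 0.756; error 2[1 − Φ(1.482)] = 13.8%.
- Linear 8 to 12.5: 105.06 + 1.83 = 106.90; s = 10.34; ratio 0.827; error 10.5%.
- Linear 10 to 12.5: 126.56 + 0.57 = 127.13; s = 11.28; ratio 0.902; error 7.7%.
- 8 rising to 12.5 by Week 8, then flat: mean square of the first 8 weeks is 10.25² + (4.5²/12)(9/7) = 107.23; overall (8 × 107.23 + 16 × 156.25)/24 = 139.91; s = 11.83; ratio 0.946; error 6.4%.
- Flat at 12.5: ratio 1.00; error 5%.
- Falling 15 to 12.5: s = 13.77; ratio 1.10; error about 3%, so the interval is too wide.

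Fitting AR(1) and Toeplitz as well, with an assumed between-week correlation of 0.6 + 0.4 × 0.8^lag, changed the linear results very little (8 to 12.5: 0.83 for all three). The levelling-off case became 0.92 for both. Allowing for other rates of levelling off, about 0.91–0.96 is a fair working range for that shape, not a bound.

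The opposite error appears early. For linear paths starting at 6 to 10, the Week 1 standard error is 9.45/6 = 1.58 to 11.28/10 = 1.13 times its correct size.

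**The only weekly spread in the documents.** SAP Appendix 1, Table 7 gives Phase 2 standard errors of the weekly score level (no diaries missing): 3.092 at Week 1, 3.842 at Week 8, 2.388 at Week 14. Their root mean square over 14 weeks is 2.99. One common value would be 2.99/2.388 = 1.25 times the Week 14 figure and 2.99/3.842 = 0.78 of the Week 8 figure.

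**The case against.** A reader might infer that late-week intervals will come out too small. The documents do not show it. The only SD of change is for Weeks 23–24, and the one weekly series, Table 7, drifts down rather than up. Table 7 does not settle the reverse either: it shows score level and not change, uses only weeks with all seven diaries, gives no n per week, and comes from another study. The objection stands as to direction.

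A reader might also infer that the controlled error rate rises to 8–14%. It does not. Weekly TSS is tested only after both co-primaries and every earlier secondary have succeeded. If there is no effect at Weeks 23–24, the ANCOVA co-primary, which does not use this model, lets the sequence continue at most about 5% of the time. Nothing follows weekly TSS, so no error carries forward.

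Third, 300 parameters for about 160 patients does not show that the unstructured fit will fail. The data are complete after imputation, and in 500 simulated complete data sets of 160 subjects and 24 weeks the unstructured estimate was always positive definite. The fallback may never be used.

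Two further points. The SAP's list reads naturally as an order already, which is fair. SAP 5.1 allows alternative methods before database lock, but under SAP 5.6 analysis starts only after the lock, when a failed fit would first appear. The single baseline slope across weeks is not part of this point: under randomization stratified by TSS its omission mainly costs precision.

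**Conclusion.** The point holds in conditional form and is minor. It is certain that every fallback named in SAP 6.12.5 forces equal variance across 24 weeks and that KR2 does not correct for this. It is conditional that harm follows: the unstructured fit must fail, and the variance of change must differ by week. The direction and size rest on an assumed SD path. For an SD rising to 12.5, the Week 24 standard error is about 0.76–0.90 of correct if the rise is linear from 6–10, and about 0.91–0.96 if it levels off early. There is no error if the SD is flat, and the Week 24 interval is too wide if it falls. The 8–14% error rate belongs to the linear-rise case and to one ungated Week 24 contrast. The co-primary TSS test is unaffected. The reach is the last-listed secondary endpoint and the exploratory analyses that refer to 6.12.5.

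**What to change.** In SAP 6.12.5, state a fixed fallback order that begins with the heterogeneous-variance forms (TOEPH, then ARH(1), then CSH) and only then moves to the homogeneous Toeplitz, AR(1) and compound symmetry. State that the same structure is used for all imputed data sets, namely the first in the order that converges in every one. If a sandwich variance is preferred instead, name a degrees-of-freedom method compatible with it in place of KR2.

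The cost is a few lines of SAP text and a change of covariance type in the code. Each heterogeneous form carries 23 more parameters than its homogeneous version, still far fewer than 300, and intervals may be wider in high-variance weeks. A heterogeneous form is not guaranteed to converge where the unstructured one fails, which is why the homogeneous forms stay at the end of the list.

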15.1 Sample Size

A total of approximately 160 patients will be enrolled.

First Co-Primary Endpoint: A sample size of 80 patients per treatment group will have >99% power to demonstrate a greater proportion of responders in AK002 patients than in placebo patients, assuming the proportions of responders are 0.6 and 0.1 in AK002 and placebo groups, respectively.

Second Co-Primary Endpoint: A sample size of 80 patients per group will provide 96% power to detect a statistically significant difference between AK002 and placebo in the mean reduction from baseline in TSS score, assuming a mean reduction of 16.1 points on AK002 versus 8.7 points on placebo and a common standard deviation of 12.5 points (AK002-003 data on file). Eighty patients per group will provide 96% power to pick up a difference between placebo and AK002 of 7.4 in TSS with a mean Baseline TSS of 30 and a standard deviation (change from baseline) of 12.5. These assumptions are based on data observed in the Phase 2 AK002-003 study.

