15.6.2 Secondary Efficacy Endpoint Analysis

If both tests of the co-primary endpoints are statistically significant, the hypothesis tests for the secondary endpoints will proceed sequentially in a prespecified order specified in the synopsis. If at any point, the statistical test is not significant at 2-sided $\alpha=0.05$ level, the hypothesis testing procedure will stop.

For patients who provide gastric or duodenal only biopsy, the calculation will be based on the average count of the highest readings from the respective mucosa at baseline and Day 169 (Week 24). For patients who provide both gastric and duodenal biopsies, the calculation will be based on the average count of the highest readings from the Day 169 biopsy that correspond in location (gastric or duodenal) to the location with the highest average count at baseline. The change in tissue eosinophil count from baseline to Day 169 will be analyzed using ANCOVA

with treatment as a factor, and baseline eosinophil counts, Baseline PRO TSS, and disease status as covariates. The LSM, SE, and 95% CI for individual treatment groups, and LSM, SE, 95% CI, and p-value for the between treatment difference will be presented.

Proportion of patients achieving gastric and/or duodenal eosinophil count of ≤ 1 cell/hpf will be analyzed using Fisher's exact test similar to the analysis for the first co-primary endpoint.

Proportion of treatment responders defined by $>30\%$ improvement in TSS **and** mean eosinophil count ≤ 4 cells per hpf in 5 gastric hpf and/or mean eosinophil count ≤ 15 cells per hpf in 3 duodenal hpf will be analyzed using Fisher's exact test.

Proportion of patients with $\geq 50\%$ reduction and $\geq 70\%$ reduction in TSS from baseline to Weeks 23–24 will be analyzed using the CMH test stratified by the randomization stratification factors.

Change in weekly TSS will be analyzed using the MMRM model. The model will include fixed effects for baseline value, treatment, week, and the treatment by week interaction and allow for random subject effects and assume an unstructured covariance structure. The Kenward-Rogers approach for computing denominator degrees of freedom will be used to account appropriately for pooling of within and between-subject variance estimates. The LSM and the 95% CI for the between group difference will be estimated for each week.

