6.11.4 Analysis of the Second Co-Primary Endpoint

The second co-primary endpoint will be analyzed by ANCOVA (primary analysis) using the imputed data set (Section 5.4.2). The LS mean, SE, and 95% CI for each treatment group and for the between group difference will be derived from ANCOVA with treatment as factor, baseline PRO TSS (continuous) and disease strata (EG \pm EoD, EoD) as covariates. The hypothesis test for the treatment effect will be carried out by the F-test. The synthesizing method will be used to combine the results from multiple imputations.

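### The weekly-TSS mixed model has no baseline-by-week term; if the correlation with baseline decays over follow-up, the late-week contrasts lose some precision

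*SAP*

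**What the plan says.** The SAP's sample code in 6.12.5 is "model CHG = B_TSS DISEASE_STRAT TRTPN WEEK TRTPN*WEEK / ddfm=KR2". The prose there names the same terms, and Protocol 15.6.2 agrees: "The model will include fixed effects for baseline value, treatment, week, and the treatment by week interaction". The main-effect baseline term is therefore the plan, not a slip in the sample code.

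The other relevant features of SAP 6.12.5 are:
- **Response:** "The model will use change from baseline in the weekly TSS from Weeks 1 through Week 24".
- **Covariance:** "The model variance-covariance matrix will be unstructured", with simpler structures only if the fit fails to converge.
- **Output:** "The LSM and 95% CI for the between group difference will be estimated using the simple contrast at each week". No week is singled out for the hypothesis test.
- **Missing data:** "Prior to the analysis, the missing weekly TSS scores will be imputed similarly to the imputation for the missing biweekly PRO TSS scores". Each imputed data set is therefore complete.

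The second co-primary endpoint is analysed separately (SAP 6.11.4) by "ANCOVA with treatment as factor, baseline PRO TSS (continuous) and disease strata". That model is fitted to Weeks 23–24 alone and so has its own baseline slope.

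SAP 5.8 tests the secondary endpoints in the order of SAP 2.2, where change in weekly TSS comes last of six.

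**The concern.** The slope of change on baseline at week t equals r_t × SD_t / SD_0 − 1. Here r_t is the correlation of that week's score with baseline, SD_t is that week's SD and SD_0 is the baseline SD. One slope for all weeks requires r_t × SD_t to be constant. Baseline TSS is the mean of the last two weekly scores before dosing (SAP Table 2), so Week 1 is adjacent to it and Week 24 is far away. If the correlation falls with distance, the true slope steepens. The pooled slope then settles between the early and late values, and part of the baseline dependence stays in the late-week residuals. The late-week intervals are wider than they need be, while early weeks are somewhat over-adjusted.

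The SAP gives no reason for a constant slope. It is also more restrictive here than elsewhere. The multivariate imputation model in SAP 5.4.2 lets the relation with baseline differ at each time point, and the ANCOVA in 6.11.4 estimates a slope for its own period.

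**Working it through.** **1. The plan's own figure.** No precision or power is stated for the weekly model. The only TSS figure is the 96% power of the second co-primary endpoint (80 per arm, difference 7.4, SD 12.5; SAP 3.5), which rests on "assuming a mean reduction of 16.1 points on AK002 versus 8.7 points on placebo" (Protocol 15.1).
- SE = 12.5 × √(2/80) = 1.976.
- 7.4/1.976 = 3.744, and Φ(3.744 − 1.960) = 0.963. The t distribution gives 0.961.

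The 96% reproduces. It belongs to the co-primary ANCOVA and does not change with the point made here.

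**2. Formulae for the weekly model.** Take complete data, an unstructured covariance and n = 80 per arm. Let β_t be the true slope at week t, S the residual covariance around those slopes, and V_0 the baseline variance.
- Pooled slope: b = (1′S⁻¹β)/(1′S⁻¹1).
- Contrast variance with one slope: (2/n) × [S_tt + (β_t − b)² × V_0].
- Contrast variance with B_TSS*WEEK: about (2/n) × S_tt × (1 + 1/156).

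**3. Assumptions.** The documents give neither the baseline SD nor any correlation of baseline with later weeks. These were assumed and varied. Each case is scaled so that the SD of change at Weeks 23–24 is 12.5.

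**4. One case in full** (correlation 0.78 at Week 1, 0.36 at Week 24). The between-week variance is split into a persistent share of 0.3, a share of 0.5 decaying by a factor of 0.9 per week, and noise of 0.2.
- The two-week baseline mean has variance share 0.3 + 0.5 × (1 + 0.9)/2 + 0.2/2 = 0.875. Scaling gives a baseline SD of 11.3 and a weekly SD of 11.3/√0.875 = 12.08.
- β at Week 24 = 0.36 × 12.08/11.3 − 1 ≈ −0.61. At Week 1 it is −0.17. The pooled slope is b = −0.32.
- S at Week 24 = 12.08² × (1 − 0.36²) = 127.0.
- Week-specific slope: SE = √(127.0 × 2/80) = 1.78, or 1.79 with the 1/156 cost.
- One slope: the extra variance is 0.29² × 11.3² = 10.7, so SE = √(137.7 × 2/80) = 1.86.
- Net ratio: 1.856/1.788 = 1.038, a 3.8% larger SE.

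**5. Range at Week 24** (weekly SD constant; SE columns before the 1/156 cost; last column after it, from unrounded values):

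| Baseline correlation, Week 1 → 24 | True slope, Week 1 → 24 | Pooled slope | SE, one slope | SE, slope by week | Net SE change from omitting the term |
|---|---|---|---|---|---|
| 0.48 flat | −0.43 → −0.43 | −0.43 | 2.24 | 2.24 | −0.3% |
| 0.79 → 0.46 | −0.16 → −0.51 | −0.28 | 1.91 | 1.86 | +2.6% |
| 0.78 → 0.36 | −0.17 → −0.61 | −0.32 | 1.86 | 1.78 | +3.8% |
| 0.75 → 0.16 | −0.19 → −0.82 | −0.43 | 1.75 | 1.64 | +6.3% |
| 0.88 → 0.36 | −0.09 → −0.63 | −0.22 | 1.85 | 1.70 | +8.4% |
| 0.88 → 0.17 (extreme) | −0.09 → −0.83 | −0.25 | 1.80 | 1.57 | +14.9% |

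If the weekly SD also grows by 20% over follow-up, the 0.79 → 0.46 case falls to +0.9% and the extreme case to +10.8%. With flat correlation of 0.48 and growing SD, Week 24 is slightly over-adjusted (pooled −0.39 against −0.31) with almost no change in SE (2.42 against 2.41).

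**6. Validity.** The flat case and the three decay cases down to 0.75 → 0.16 were simulated, 1,500 trials each. Mean estimates lay between −7.28 and −7.45 under both models, against a true −7.4. Coverage with one slope was 0.949 to 0.955. In the 0.78 → 0.36 case the mean SE was 1.85 against 1.78, matching the formula.

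**The case against.** The strongest objection is that the result hangs on the early slope, which the documents do not give and may even suggest is already steep. The Phase 2 summary in Protocol 2.3 reports symptom improvement within 24 hours of the first dose. Every patient takes 60 mg prednisone before Day 1, and entry on symptom thresholds invites regression to the mean from the first week. Take a late slope of about −0.41, the mean of 16.1/30 = 0.54 and 8.7/30 = 0.29. This is itself an assumption, since these are ratios of group means and not regression slopes. With a baseline SD of 10 to 12, the net variance penalty at Week 24 is:
- 4–24% if the Week 1 slope is −0.1;
- 1–11% if it is −0.2;
- 0–2% if it is −0.3;
- none if it is −0.4, where the added term costs about 0.6% of variance (0.3% of SE).

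This stands, and it is why the point is conditional and its range includes zero.

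It is also fair that a main-effects model is a valid prespecified choice, stated consistently in both documents, and that little rides on it. Illustrative power for 7.4 points at Week 24 in the 0.78 → 0.36 case is 97.9% against 98.6%. Stratifying randomization on screening TSS at 28 limits actual baseline imbalance.

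A reader might infer that the Week 23 and 24 contrasts ought to match the co-primary result and that the pooled slope prevents this. The documents do not support that. SAP 6.12.5 reports single weeks from imputed weekly scores, whereas the co-primary uses a two-week average that is missing if either week is missing and is imputed from biweekly scores. The two can differ even with identical baseline adjustment.

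**Conclusion.** The point holds as a conditional matter of efficiency. One baseline slope is imposed on all 24 weeks. If the correlation with baseline decays, the Week 24 SE is about 1% to 8% larger than necessary in most scenarios examined and 11% to 15% larger in the extreme one. If the slope is constant, nothing is lost. The figures assume complete data after imputation and an unstructured covariance; the fallback structures were not examined.

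A reader might go further and conclude that the late weeks are in fact under-adjusted, that the treatment estimates are biased, or that type I error is at risk. The first needs correlations that the documents do not contain. The other two find no support: treatment is randomized, the unstructured covariance absorbs the misfit, and estimates and coverage were sound in simulation. Nor should the loss be expressed as patients wasted, because the trial was sized on the co-primary endpoints and not on this model.

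The co-primary ANCOVA and the sample size are untouched. The severity is low: a cheap improvement to the last-ranked secondary endpoint.

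**What to change.** Add B_TSS*WEEK to the MODEL statement and to the list of model terms in SAP 6.12.5, or state there why a constant slope is assumed. The change needs one line of text and code and no new data. It replaces one slope by 24, which adds 23 fixed-effect parameters to a 24-week unstructured model in about 160 patients. If the term is not needed, it costs about 0.3% of the SE.

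The sponsor can judge the likely gain beforehand from the 14 weeks of Phase 2 daily diaries already used in SAP Appendix 1, by estimating the slope of change on baseline week by week. The change should be made before unblinding. Some exploratory analyses in SAP 6.13 refer back to 6.12.5, so the SAP should say whether they inherit the term.

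A disease-stratum-by-week term is not part of this recommendation, because nothing was calculated to support it.
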